Hypothesis: Early administration of insulin glargine will result in a lower incidence of rebound hyperglycemia, defined as blood glucose > 180 mg/dL in the 24 hours after IV insulin infusion discontinuation, when compared to usual care for the treatment of diabetic ketoacidosis?

- 6) What is the prevalence of a hypoglycemic (defined as blood glucose < 70mg/dL) event occurring while on IV insulin therapy or in the 24h hours after IV insulin infusion discontinuation with early insulin glargine administration compared to usual care?

Hypothesis: The occurrence of a hypoglycemic event occurring while on IV insulin therapy or in the 24h hours after IV insulin infusion discontinuation with administration of insulin glargine is comparable to usual care.

- 7) Does early administration of insulin glargine result in a statistically lower mean blood glucose value in the 24 hours and (separately) 48 hours after IV insulin infusion discontinuation?

Hypothesis: Early administration of insulin glargine will result in a lower mean value of blood glucose in the 24 and 48 hours after IV insulin infusion discontinuation.

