### Sample size

From 1/1/2018 to 6/30/2019 there were 399 unique encounters of patients admitted to Regions Hospital with an associated ICD-10 code of E10.10 (Type 1 diabetes mellitus with ketoacidosis without coma), E10.11 (Type 1 diabetes mellitus with ketoacidosis with coma), E11.10 (Type 2 diabetes mellitus with ketoacidosis without coma),

E11.11 (Type 2 diabetes mellitus with ketoacidosis with coma), E13.10 (Other specified diabetes mellitus with ketoacidosis without coma), or E13.11 (Other specified diabetes mellitus with ketoacidosis with coma).

We expect patients to present at the same rate, indicating that an estimated 264 patients with one of these eligible diagnoses will present over the twelve months of study enrollment. Of those 264, we expect 25% to be ineligible due to meeting one of the study exclusion criteria and another 25% to be eligible but decline participation. Therefore, we expect to see 132 total eligible subjects (66 in each randomization arm). Due to our fixed sample-size, in lieu of a traditional power analysis to determine the number of subjects needed to detect a difference between the group we plugged our fixed sample size into a power analysis and solved for length of stay.

We ran a power analysis using the same historical data used under the Sample size section of this proposal. Because we expect about 132 patients to be enrolled, we inspected length of stay (LOS) from the first 100 cases in our historical data. LOS is heavily right-skewed, so we log-transformed it to estimate detectable effect size. We used the “proc power” program in SAS 9.4, which has specifications for comparing two log-transformed means. In order to achieve 80% power to detect a true difference between two fixed groups of  $n=66$ , the ratio of logs would have to be about 1.31; when normalized, this translates to about 6.5 hours ( $\alpha = 0.05$ , coefficient of variation = 0.6). So, with our sample size, we estimate that the intervention would need to cause a 6.5-hour difference in average length of stay between groups in order for us to detect a difference 80% of the time.

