### Variable list, sources, and data collection

The variables listed on the below data collection form will be incorporated into a secure REDCap database that research staff will use to enter the data. Patients will be assigned study ID numbers in the REDCap database. The REDCap database will contain identifying information, however, if de-identified data needs to be shared outside of the direct study team, the dataset can be downloaded without identifying variables such as MRN.

Variable Name	Role of Variable	Measurement Scale
Study ID	Unique identifier	Continuous (001 – n)
MRN	Link to EMR	String
Full name	Link to EMR	String
Date of ED presentation	Link to EMR	DMY
Age	Descriptive	Continuous
Race	Descriptive	Categorical, as reported in Epic
Ethnicity	Descriptive	Categorical, as reported in Epic
Sex at birth	Descriptive	Categorical, as reported in Epic
End stage renal disease or hepatic disease	Inclusion/exclusion criteria	Binary
Vasopressor dose to treat hypotension at any point during admission	Inclusion/exclusion criteria	Binary
On insulin pump therapy at baseline (prior to ED)	Inclusion/exclusion criteria	Binary
On combination insulin products (i.e. Novolin® 70/30, Novolog® 70/30, Humalog® 75/25, etc.) at baseline	Inclusion/exclusion criteria	Binary
Presenting pH (prior to intervention)	Inclusion/exclusion criteria	Continuous

Time of first pH	Calculate time to resolution	Continuous
Time of short-acting insulin start	Calculate time to resolution	Continuous
Time of first pH > 7.3	Outcome Calculate time to resolution	Continuous
Presenting blood glucose in mg/dL	Inclusion/exclusion criteria	Continuous
Time of first blood glucose < 250 mg/dL	Outcome Calculate time to resolution	Continuous
Blood glucose > 180 mg/dL in the 24 hours after IV insulin infusion discontinuation	Outcome	Binary
Blood glucose < 70mg/dL $\geq$ 1 time at any point while on IV insulin therapy or in the 24 hours after IV insulin infusion discontinuation	Outcome Prevalence of AE (hypoglycemia)	Binary
Blood glucose < 70mg/dL at any point between glargine start and 24 hours after IV insulin infusion discontinuation (control group only)	Outcome Prevalence of AE that may be contributable to study intervention (hypoglycemia)	Binary
Mean blood glucose in 24 and 48 hours after IV insulin infusion discontinuation	Outcome	Continuous
Presenting anion gap	Inclusion/exclusion criteria	Continuous
Time of first anion gap	Calculate time to resolution	Continuous

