### Statistical analysis plan

The primary outcome and secondary outcomes 1-4 and 7 will follow the same analysis plan to study the difference in the distribution of time to an endpoint. First, the distributions for each of these outcomes will be evaluated to determine if the distribution is normal or non-parametric. If the distribution is normal, that outcome will be analyzed using a two-tailed unpaired t-test. If the distribution is non-parametric, that outcome will be analyzed using a Wilcoxon rank sum test. We expect length of stay data to follow a non-parametric distribution. In secondary outcome 2, the outcome measured is the time at which all of the necessary criteria are hit for the first time simultaneously, which accounts for the transient nature of some of these measures.

Secondary outcomes 5-6 will measure the prevalence of each of these outcomes. Prevalence was chosen over incidence in order to account for multiple instances of rebound hyperglycemia or hypoglycemia occurring within the specified timeframe for each and also the amount of time it takes to clinically reverse these conditions. For both of these outcomes, a two-proportion z test will be run to find the difference in the amount of time each treatment arm cumulatively spent with the specified condition. Finally, for the outcomes relying on certain lab values, we will examine time from IV insulin infusion start to outcome labs in both groups. If there is significant variability between the experimental and SOC arms, we will adjust for this statistically. Group randomization should ensure that variability is

equally distributed between groups, however, there is a chance of bias (e.g., if the experimental group fares better and thus are slower to get nursing checks.)

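### Hypoglycemia is hypothesised to be comparable between arms, but the only planned analysis is a test of difference, with no margin or confidence interval; a non-significant result would not exclude a sizeable excess

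*Combined protocol and SAP*

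**What the plan says.** Under Study aims, the question for secondary outcome 6 asks how common a glucose below 70 mg/dL is, during IV insulin or in the 24 hours after it stops, "with early insulin glargine administration compared to usual care". The hypothesis is that this occurrence "with administration of insulin glargine is comparable to usual care". The hypotheses for the primary outcome and the other secondary outcomes all predict a shorter, faster or lower result in the glargine arm.

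The Statistical analysis plan treats outcomes 5 and 6 together: "a two-proportion z test will be run to find the difference in the amount of time each treatment arm cumulatively spent" with the condition. No other between-arm comparison is specified for outcome 6. The Variable list, however, holds a yes/no field per patient (at least one glucose below 70 mg/dL in the same window), labelled "Outcome Prevalence of AE (hypoglycemia").

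The Sample size section says "we expect to see 132 total eligible subjects (66 in each randomization arm"). Its only power statement concerns length of stay. Nowhere is there a margin, an equivalence or non-inferiority test, a confidence interval, or a power or precision statement for hypoglycemia.

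**The concern.** A test of no difference can reject equality; it cannot establish similarity. With few events and 66 patients per arm, p > 0.05 is compatible with no excess and also with a sizeable one. The stated hypothesis therefore has no analysis that could support it.

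This matters because the Risks and Benefits section names hypoglycemia as the potential risk and says that basal and IV insulin will overlap for longer. The Setting section gives safety as a purpose of the study, and the Dissemination section hopes that the data will shape future treatment policy. If non-significance were taken as comparability, a safety conclusion could rest on absence of evidence.

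**Working it through.** **1. The plan's own power figure.** The Sample size section gives a detectable length-of-stay ratio of about 1.31 (80% power, alpha 0.05, coefficient of variation 0.6, 66 per arm).
- Log-scale SD = √ln(1 + 0.6²) = 0.5545.
- SE of the difference = 0.5545 × √(2/66) = 0.0965.
- Detectable ratio = exp[(1.960 + 0.842) × 0.0965] = 1.31.

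The figure reproduces. It says nothing about hypoglycemia.

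**2. Inputs for hypoglycemia.**
- n = 66 per arm (Sample size).
- Outcome: the per-patient yes/no field (Variable list). This is not the cumulative-time quantity named in the Statistical analysis plan, whose denominator is undefined, so no power can be computed for that test.
- Two-sided alpha 0.05. This is an assumption: the plan gives 0.05 for length of stay and two tails for the t-test, but neither for the z test.
- Control risks from the studies summarised in the Background. 55% is printed for the late group of the 2019 retrospective cohort. 25% is 5 control patients out of an assumed 20 in the 2015 single-center trial of 40. 15% is 3 control events out of an assumed 20 in the 2015 two-center trial of 40, also assuming one event per patient.

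**3. Precision if the observed rates are equal.** Half-width = 1.96 × √[2p(1 − p)/66].
- p = 0.15: 1.96 × 0.0622 = 12.2 points.
- p = 0.25: 1.96 × 0.0754 = 14.8 points.
- p = 0.55: 1.96 × 0.0866 = 17.0 points.

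**4. Power for a true excess.** Power = Φ{[d − 1.96 × √(2p̄(1 − p̄)/66)] / √[(p₁(1 − p₁) + p₂(1 − p₂))/66]}, where d = p₂ − p₁ and p̄ is the mean of the two risks. For 15% vs 25%: (0.10 − 1.96 × 0.0696)/0.0691 = −0.53, so power is 30%.

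| Control risk | Power, +10 points | Excess detectable with 80% power |
|---|---|---|
| 15% | 30% | 21 points |
| 25% | 24% | 23 points |
| 55% | 21% | 23 points |

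Relative increases, by the same formula:
- 15% to 22.5%: 19.5%
- 25% to 37.5%: 34%
- 15% to 30%: 54%
- 25% to 50%: 85%
- 55% to 82.5%: 93.5%

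**5. Results that would be non-significant** (pooled z test, Newcombe 95% interval).
- 10/66 vs 19/66: difference +13.6 points, p = 0.058, upper limit about +27 points.
- 16/66 vs 26/66: difference +15.2 points, p = 0.062, upper limit about +30 points.

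**The case against.** **No decision rule is written.** A reader might infer that p > 0.05 will be reported as proof of safety. The documents do not say so: the analysis plan says only that a difference will be sought, and the aim is phrased as a question about prevalence. The inference is fair, because the Summary and Background already describe small earlier studies as showing no added hypoglycemia. But it supports only that the result could be misread, not that it would be.

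**The power figures are not for the planned test.** This stands. They describe the per-patient field. A z test that treated units of time as independent observations might reject too often rather than too seldom.

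**Low power is not general.** A reader might also infer that the trial has little chance of detecting any clinically large increase. That is too strong: 25% to 50% has about 85% power and 55% to 82.5% about 93.5%. Power is low for excesses of around 10 points.

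**Earlier data point the other way, and the aim is modest.** Each earlier study summarised in the Background has numerically less hypoglycemia with early basal insulin, so the excesses modelled here are hypothetical. The trial calls itself a small pilot, and outcome 6 is one of seven secondary outcomes. This limits the severity. It does not supply an analysis that could support the stated hypothesis.

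**Conclusion.** The point holds: outcome 6 states a hypothesis of similarity and is given only a test of difference. The missing interval and margin are a gap at any event rate; how much a non-significant result leaves open depends on the rate. Under the assumptions above, equal observed rates still leave about 12 to 17 points of excess within the interval, and a true 10-point excess would be detected 21% to 30% of the time. At a 5% control risk, which the Background does not suggest, the half-width would still be about 7 points.

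The point concerns what a non-significant result can support. It does not show that hypoglycemia will increase, nor that the investigators will claim safety from such a result. For a secondary outcome in a trial of this size the change should be made, but the gap does not undermine the trial's primary comparison.

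**What to change.** In the Statistical analysis plan, for outcome 6:
- Analyse the proportion of patients with at least one glucose below 70 mg/dL in the stated window, using the existing field that covers both arms, in place of cumulative time.
- Report the risk difference with a 95% confidence interval, and state the largest excess that the interval does not exclude.
- State that p > 0.05 will not be taken as comparability.

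If the investigators still want to claim comparability, they should set the margin themselves before data are seen, on clinical grounds, and make the claim only if the upper limit lies below it. With 66 per arm and equal true risks, the smallest margin supported with 80% power (one-sided 0.025) is 2.80 × √[2p(1 − p)/66]: 17.4, 21.1 and 24.3 points at 15%, 25% and 55%. A formal claim may therefore be out of reach.

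The interval and the rule on interpretation need only a change of SAP wording, with no new data or patients; a margin would also need a clinical judgement. The downside is that the safety conclusion will probably be weaker than comparable at this sample size.

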## **Background, Rationale, Significance**

In 2014, there were 168,000 hospitalizations for DKA, and the average length of stay was 3.4 days in 2009. The estimated annual direct medical expense and indirect cost is 2.4 billion dollars per year. DKA is a potentially life-threatening condition due to its ability to cause metabolic acidosis, electrolyte imbalances, and dehydration. While DKA treatment protocols differ from institution to institution, the goals of treatment remain the same --- resolution of acidosis, dehydration, and hyperglycemia. Following fluid resuscitation, correction of hyperglycemia with insulin therapy is the mainstay of treatment. Intravenous (IV) insulin infusions with regular insulin are commonly used due to its short half-life of 30 to 60 minutes and resulting titratability. Treatment is then continued with subcutaneous (SC) insulin once the acidosis and anion gaps have cleared and the patient's hemodynamics and electrolytes abnormalities have resolved. At Regions Hospital, the current criteria for transitioning from IV to SC insulin include meeting the following criteria: 1) fasting blood glucose levels are stable between 180-250 mg/dL for at least 4 hours, 2) vital signs, potassium, and sodium levels are stable and within the normal range, 3) the metabolic acidosis has cleared (anion

gap  $<15$ , and either arterial pH  $\geq 7.3$  or venous pH  $\geq 7.27$ ), and 4) the patient is able to eat regular meals. Traditionally, when SC insulin is initiated, the IV insulin infusion is stopped two hours later. However, the timing of SC initiation has becoming more controversial in recent years. The 2019 American Diabetes Association Standards of Care recommend transition of patients from IV to SC insulin requires administration of basal insulin 2–4 h prior to the intravenous insulin being stopped to prevent recurrence of ketoacidosis and rebound hyperglycemia. However, the 2014 Joint British Diabetes Societies Inpatient Care Group recommend continuing a patient's home basal insulin during the initial management of DKA to prevent rebound hyperglycemia and to avoid extending length of stay. Several recent papers have examined early basal insulin administration as adjunct therapies with IV insulin infusions for the treatment of hyperglycemia and DKA.

In 2012, a single-center prospective, randomized controlled trial by Hsia et al. compared IV insulin infusion with or without early administration of insulin glargine (dose = 0.25 U/kg) in 61 hyperglycemic patients with diabetes. Forty-one percent (25/61) of the patients enrolled in the trial were admitted with DKA. Those in the early insulin glargine arm were to receive the glargine subcutaneous injection within 12 hours of initiation of IV insulin infusion. Patients were excluded if they were newly diagnosed with hyperglycemia, critically ill, or pregnant. All other decisions about transitioning study subjects to SC insulin was left to primary teams including dose, type of insulin, and timing of transition. Those patients that received early glargine had lower prevalence of rebound hyperglycemia when the insulin infusion was discontinued (experimental group: 33% vs control group: 93.5%;  $P < 0.001$ ). The total length of IV insulin infusion was similar in the two groups (control group:  $35 \pm 13$ h vs experimental group:  $42 \pm 24$ h). The mean blood glucose levels within the 12-hour study period were significantly lower in the intervention group, while there were 3 asymptomatic hypoglycemic measurements in the control group and none in the intervention group.

In 2015, Doshi et al. conducted a two-center prospective, randomized controlled trial of 40 patients admitted for DKA. Patients were randomized to receive early insulin glargine (dose = 0.3 U/kg) or no glargine in addition to regular care. Those in the early insulin glargine arm were to receive the glargine subcutaneous injection within 2 hours of diagnosis. Patients were excluded if they required inotropic/vasopressor resuscitation, had ESRD, required emergent surgery, or were less than 18 years old, pregnant, unwilling to participate, prisoners, or transferred to another hospital. Patients in the control group were given insulin glargine once the anion gap closed and the IV insulin infusion was continued for two additional hours. There was no difference in time to anion gap closure (control group:  $11.6 \pm 6.4$ h vs experimental group:  $10.2 \pm 6.8$  hours;  $p = 0.63$ ), hospital length of stay (control group:  $4.6 \pm 3.6$  days vs experimental group:  $3.9 \pm 3.4$  days;  $p = 0.66$ ), ICU admissions (control group: 4 admissions vs experimental group: 6 admissions;  $p = 0.71$ ), ICU length of stay (control group: 1.2 days vs experimental group: 1.8 days;  $p = 0.47$ ), and hypoglycemic events (control group: 3 events vs experimental group: 2 events).

Also in 2015, Houshyar et al. conducted a single-center, prospective, randomized controlled trial of 40 patients admitted for DKA. Patients were randomized to receive early insulin glargine (dose = 0.4 U/kg) or no insulin glargine in addition to usual care. Those in the early insulin glargine arm were to receive the glargine subcutaneous injection within 3 hours of IV insulin infusion initiation. Patients were excluded if they had hypotension (systolic blood pressure  $< 80$  mmHg despite receiving 1000ml NS), acute MI, progressive renal or hepatic failure, or lack of consent. Patients in the control group were given insulin glargine once the anion gap closed. There was no difference in duration of acidosis (control group:  $16.91 \pm 6.5$ h vs experimental group:  $13.77 \pm 6.1$ h;  $p = 0.123$ ). There were higher rates of hyperglycemia following discontinuation of the insulin infusion in those that did not receive early glargine (51% vs. 35% of measurements in the experimental group showed a glucose  $>8.3$  mM or  $>150$  mg/dL;  $p = 0.046$ ). There was no difference in hospital length of stay (control group:  $5.9 \pm 2.2$  days vs experimental group:  $5.1 \pm 1.9$  days;  $p = 0.225$ ) or rates of hypoglycemia (control group: 7 events in 5 patients vs experimental group: 4 events in 4 patients; no p-value reported).

Lastly, Rappaport et al. (2019) conducted a single-center, retrospective cohort study of 106 admissions for DKA comparing early vs late initiation of basal insulin. Patients admitted to the MICU who were treated with home-dose basal insulin prior to DKA resolution and within 24 hours of IV insulin infusion initiation ( $n = 33$ ) were compared to patients who were initiated on basal insulin within 6 hours before or any time after IV insulin infusion discontinuation ( $n = 73$ ). Transition from IV insulin infusion to subcutaneous insulin was not addressed in a protocol and was left to the discretion of the provider. Patients were excluded if they had surgery within 48 hours of IV insulin infusion, were pregnant, were in vasopressor dependent shock, or had another indication for insulin therapy. Patients in the early group had initial daily doses of basal insulin of 0.48 U/kg (IQR: 0.34 – 0.62) compared to 0.44 U/kg in the late group. Patients in the early insulin group had their first dose of basal insulin 2.5 hours (IQR: 0.4 – 6.4) after IV insulin infusion initiation. There was no difference in transitional failure (early group: 6% vs late: 10%;  $p = 0.717$ ), rebound hyperglycemia (early: 81% vs late: 88%; OR: 0.59, CI: 0.16 – 2.25), hypoglycemia events (early: 33% vs late: 55%; OR: 0.41, CI: 0.16-1.05); time to anion gap closure: (early: 7.8h vs late: 9.1h;  $p = 0.73$ ), length of ICU stay (early: 34h vs late: 33.3h,  $p = 0.83$ ), or hospital length of stay (early: 2 days vs late: 2 days,  $p = 0.9$ ). There was a statistically significant decrease for time on IV insulin infusion (early: 13.8h vs late: 17.1h,  $p = 0.04$ ).

Preliminary research at Regions Hospital determined that in 40 randomly selected patients admitted for DKA in 2019, the mean dose of basal insulin initiated was 0.39 units per kilogram, and it was administered a mean of 22.4 hours after initiation of the IV insulin infusion and 1.86 hours prior before discontinuation of IV insulin, which is consistent with ADA recommendations

In summary, previous randomized studies using weight based basal insulin doses have shown that the early initiation of basal insulin can prevent rebound hyperglycemia with no increase in hypoglycemia. One retrospective study demonstrated a decrease of time on IV insulin infusion in those that received early basal insulin when compared to those that did not. These studies have also shown trends toward shorter ICU and hospital length of stay, anion gap closure, and time to resolution of acidosis but none have demonstrated statistical significance. However, no prospective trials have examined resuming the patient's home basal insulin early in the course of DKA. It is currently unknown if resuming a portion or the entirety of the patient's home basal regimen will provide an impact on patient care. By conducting a prospective study comparing initiation of early glargine administration at the patient's home dose to current standards of care, early administration may lead to shorter ICU and hospital lengths of stay as well as shorter duration of acidosis. This could provide significant cost-savings to the institution and benefit patients in need of treatment for this serious complication of diabetes.

